characterize the safety profile of Mysimba. As a supplement to the Mysimba Risk Management Plan (RMP), Orexigen has designed this database study to address that request. This study will describe the utilization and safety of Mysimba/Contrave in a real-world setting using electronic health records (EHR) and administrative health claims in several European countries and the U.S. Available characteristics of patients initiating Mysimba/Contrave will be described, with particular focus on patients receiving Mysimba/Contrave in a manner noncompliant with the Summary of Product Characteristics (SmPC) at initiation, such as use inconsistent with labelled indication or use in patients with a contraindication to the medication. Use inconsistent with labelled or otherwise authorized indication includes, but is not limited to: age <18 years and use for a reason other than management of weight in a patient who has obesity or is overweight. Contraindications include, but are not limited to, the following: current diagnosis of uncontrolled hypertension, seizure disorder, or end-stage renal failure; history of seizures, bipolar disorder, anorexia nervosa or bulimia; current dependence on chronic opioids or opiate agonists (e.g., methadone); current state of acute opiate withdrawal; or any concomitant treatment containing bupropion, naltrexone, or a monoamine oxidase inhibitor (MAOI). This study also plans to evaluate the incidence of adverse events of special interest (AESI) in real-world settings. The incidence of seizures, suicidality (i.e., suicidal ideation, attempted

Mysimba/Contrave, to inform the MAH's view on the following:To further refine the risk management and pharmacovigilance planning for this product;

suicide or completed suicide), neuropsychiatric events (i.e., mania or depression), hepatotoxicity,

or severe hypersensitivity reactions following initiation of treatment with Mysimba/Contrave

will be investigated. Additionally, the incidence of AESIs will be evaluated in subgroups of

Results from this study will add further definition and clarity to the overall safety profile of

patients, including those who do not adhere to the conditions of use set out in the SmPC.

2. To determine whether the SmPC should be revised, based on the available post-marketing evidence, with the objective of optimizing the safe and effective use of the product.

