8. RESEARCH QUESTIONS AND OBJECTIVES

The aim of the study is to assess the long-term (548 days) real-world utilization patterns of Mysimba/Contrave use among patients who are prescribed Mysimba/Contrave. There are no a priori hypotheses for this study.

The primary objectives of the study are:

- To describe demographic and baseline characteristics of patients initiating use of Mysimba/Contrave; and
- 2. To evaluate patterns of Mysimba/Contrave initiation and use, including number of prescriptions, number of treatment episodes and duration between prescriptions, as well as estimating the number and percentage of patients compliant and non-compliant with the SmPC.

Analysis of compliance to the labelled indication and contraindications will be adapted to the specific SmPC for the country relevant to the data source (s). Examples of non-compliance include, but are not limited to:

Use inconsistent with labelled indication:

- 1. Age <18 years
- 2. Use other than management of weight
- 3. Management of weight in a patient who does not have obesity or is not overweight and has a weight-related comorbidity
- 4. A prescribed maintenance dose other than the Mysimba/Contrave 32mg/360mg
- 5. Continued use past 16 weeks without \geq 5% weight loss

Use in patients with contraindications:

- 6. A current diagnosis of uncontrolled hypertension, seizure disorder (or history of seizures), or end-stage renal failure
- 7. A history of bipolar disorder, anorexia nervosa or bulimia
- 8. A current dependence on chronic opioids or opiate agonists (e.g., methadone)
- 9. A current state of acute opiate withdrawal
- 10. Any concomitant treatment containing bupropion, naltrexone, or a MAOI
- 11. Patients with a known central nervous system tumour

Proprietary and Confidential:

- 12. Patients undergoing acute alcohol or benzodiazepine withdrawal
- 13. Patients with severe hepatic impairment (dependent on local SmPC)

The secondary objectives of this study are:

- 1. To assess and compare the observed incidence of AESIs in usual clinical practice among users of Mysimba/Contrave compliant and non-compliant with the SmPC. AESIs include new onset of the following:
 - 1. Seizures
 - 2. Suicidality (i.e., suicidal ideation, attempted suicide or completed suicide)
 - 3. Neuropsychiatric events (i.e., mania or depression)
 - 4. Hepatotoxicity
 - 5. Severe hypersensitivity reaction
 - 6. Serotonin syndrome

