9.3.3. Covariates

When available, the following variables needed to conduct analysis for the primary and secondary research objectives will be collected. Variable availability from each country will be summarized in the SAP and is included in Appendix 3 in draft form.

Demographics and Baseline variables (Within 365 days before index date unless otherwise stated below; as depicted in Figure 1):

- 9. Patient demographics (age and sex on index date) (obtained directly from data source)
- 10. BMI, height, weight (most recent value on or before the index date) (obtained directly from data sources; BMI may be calculated if height and weight available)
- 11. Relevant comorbidities (obtained via ICD-10 codes), including:
 - 1. Weight-related comorbidities (i.e, type 2 diabetes, dyslipidaemia, hypertension)
 - 2. Neuropsychiatric conditions (mania, bipolar disorder, major depressive disorder [MDD], anorexia nervosa, bulimia)
 - 3. Uncontrolled hypertension, if possible
 - 4. Moderate or severe renal impairment
 - 5. End-stage renal disease
 - 6. Seizure disorder
 - 7. Hepatic impairment (defined by Child-Pugh score category, if available)
 - 8. Central nervous system tumour

- 12. History of, or current substance abuse/dependencies including acute opiate withdrawal (obtained via ICD-10 codes)
- 13. History of uncontrolled hypertension, seizures, bipolar disorder, MDD, anorexia nervosa, or bulimia (obtained via ICD-10 codes)
- 14. Prior medication use, including: naltrexone, bupropion, CYP2B6 inhibitors, CYP2B6 inducers, CYP2B6 substrates, CYP2D6 substrates, Monoamine oxidase inhibitors, Opioids, Opium alkaloids and derivatives and drugs that lower seizure threshold (obtained via ATC [Nordic data] or NDC [US data]) see Appendix 2 and 2A
- 15. Pregnancy status and breastfeeding status (obtained via ICD-10 codes)

All variables will be identified from the data sources outlined below using a pre-specified list of definitions per database (Appendix 3), to be defined in the SAP as final.

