All citizens of these countries are represented in these national registries until death or emigration, providing virtually complete long-term follow-up. Identification of individuals by their unique personal identifier permits linkage to other national health databases (Laugersen et al., 2021). Thus, a large amount of specialized information from specific registries, such as hospitalization, prescription, heart disease, and death registries, can be linked for research (Schmidt 2015; Laugersen et al., 2021). The registries are highly complete and accurate due to the automation of their processes, as well as laws and other incentives motivating healthcare providers to collect and send the data electronically to their national databases (Gribsholt et al., 2019). The data from each country are expected to contain sufficient information to elucidate occurrence and determine levels of all variables, with the following exceptions which may be prone to misclassification due to limited coding in administrative and clinical data: obese or overweight with at least one comorbidity, neuropsychiatric conditions, history or current substance use or dependence, breastfeeding status, initial titration scheme and dose adjustments (expected to be unavailable since only one dose/pack type is available in the Nordic countries and no measure of titration scheme or adherence is included within the data), and reason(s) for medication discontinuation. Any country database with at least 750 patients with at least 365

days of data before the index Mysimba use and at least 548 days of availability in the data after the index date of Mysimba will be evaluated for whether there is sufficient required patient data to conduct this study. If there is sufficient data and uptake indicating that the database will reach more than 3,000 patients within the timespan of this drug utilisation and safety study, then it will be added to the data sources for evaluation. It should be noted that reimbursement varies in Scandinavia, with no reimbursement for Mysimba in Sweden and Denmark, and reimbursement in Norway and Finland restricted to morbidly obese patients who are at higher risk of cardiovascular and other events.

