9.7.2. Descriptive Statistics

For demographic and baseline variables and duration of Mysimba/Contrave use (measured as both continuous treatment of the initial Mysimba/Contrave duration and the total treatment duration of Mysimba/Contrave), descriptive statistics will be used to describe continuous variables, (e.g., mean, standard deviation, median, quartiles 1 and 3, minimum, maximum, and two-sided 95% confidence intervals [CI]). Categorical variables will be described by the total and percentage of each response and the number of missing data (data that are unavailable in the database).

Patterns of Mysimba/Contrave use will be described by mean (standard deviation, SD) and median (quartile1, quartile 3) number of prescriptions per patient, number and duration of treatment episodes per patient as well as the average duration between prescription episodes. Analyses will be performed for all users of Mysimba/Contrave, including an assessment of whether the subjects have adhered to the prescribed treatment with Mysimba/Contrave according to the terms of the SmPC (adapted to the local country SmPC for the data source as needed, and adapted if BMI is not accessible). The number and proportion of patients who received treatment with Mysimba/Contrave will be provided according to the following subgroups (availability of variables to be summarized in SAP):

(a) Inconsistent with labelled indication:

- 1) Age < 18 years
- 2) Use other than management of weight
- 3) Management of weight in a patient who does not have obesity or is not overweight and has a weight-related comorbidity
- 4) A prescribed maintenance dose other than the Mysimba/Contrave 32mg/360mg
- 5) Continued use past 16 weeks without \geq 5% weight loss
 - (b) Incompatible with the stated contraindications set out in the SmPC:
- 1) A current diagnosis of uncontrolled hypertension, seizure disorder (or history of seizures), or end-stage renal failure
- 2) A history bipolar disorder, anorexia nervosa or bulimia
- 3) A current dependence on chronic opioids or opiate agonists (e.g., methadone)
- 4) A current state of acute opiate withdrawal
- 5) Any concomitant treatment containing bupropion, naltrexone, or a MAOI
- 6) Patients with a known central nervous system tumour
- 7) Patients undergoing acute alcohol or benzodiazepine withdrawal
- 8) Patients with severe hepatic impairment

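### The 365-day default look-back in Section 9.3.3 also governs contraindications defined by any history of seizures, bipolar disorder, anorexia nervosa or bulimia, so the non-compliance percentage is biased downward

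*Protocol*

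**What the plan says.** **The capture rule.** Section 9.3.3 sets a default window for every baseline variable: "Demographics and Baseline variables (Within 365 days before index date unless otherwise stated below; as depicted in Figure 1". The history conditions are item 13: "History of uncontrolled hypertension, seizures, bipolar disorder, MDD, anorexia nervosa, or bulimia (obtained via ICD-10 codes". Item 13 gives no window of its own. Item 10 in the same list does give one: "BMI, height, weight (most recent value on or before the index date". Section 9.2 calls the 365 days before index the baseline period. Note b to Figure 1 lists the same conditions among the baseline conditions, also without a longer window.

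**The contraindications.** Section 8 lists among the examples of non-compliance "A current diagnosis of uncontrolled hypertension, seizure disorder (or history of seizures), or end-stage renal failure" and "A history of bipolar disorder, anorexia nervosa or bulimia". Section 9.7.2 repeats both as criteria (b)1 and (b)2, the second worded "A history bipolar disorder, anorexia nervosa or bulimia". Section 7 groups the conditions the same way: "history of seizures, bipolar disorder, anorexia nervosa or bulimia". None of these places limits how far back the history reaches.

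**Where the classification is used.** Primary objective 2 estimates the number and percentage of patients compliant and non-compliant with the SmPC. The first secondary objective in Section 8 compares AESI incidence between the two groups.

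**The concern.** The definition and the capture rule do not match. A contraindication defined by any history is met by a patient last coded for bulimia 18 months before index, yet the 365-day window does not see that code. If nothing else marks the patient as non-compliant, the patient joins the compliant group.

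Shortening the look-back can only lose true history on these criteria and cannot add any, so the error runs in one direction. It falls on the percentage that primary objective 2 exists to estimate. A second effect follows only if these histories raise AESI risk: the misplaced patients then raise the rate in the compliant group and narrow the contrast.

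**Working it through.** The protocol states no figure that depends on this look-back, so there is nothing to reproduce. The check is a reading of the text, followed by arithmetic on assumed inputs.

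**Reading**

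1. The default applies unless an item states otherwise. Item 10 shows how an exception is written in this list, and item 13 contains none. The default therefore governs item 13.
2. Sections 7, 8 and 9.7.2 use history without a limit. No section asks for ever-before or all-available history.
3. The 365 days of records required for entry (Section 9.1.1) are a minimum. They do not instruct anyone to use older records.
4. The data do not force the short window. Section 9.4.1 says the Nordic records cover nearly all residents for as long as they live in the country, and Section 9.4.2 includes medical history and problem lists in the US extract.

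**Share captured (all inputs assumed, none from the protocol)**

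Lifetime prevalence among users: bipolar disorder 2%, seizures 2%, eating disorder 1.5%, in total 5.5 percentage points if overlap is ignored. Probability of a code in the last 365 days: 50-80%, 30-60% and 5-20% respectively.

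- Low: 2 × 0.50 + 2 × 0.30 + 1.5 × 0.05 = 1.675 points; 1.675 / 5.5 = 30%.
- High: 2 × 0.80 + 2 × 0.60 + 1.5 × 0.20 = 3.10 points; 3.10 / 5.5 = 56%.
- Missed: 5.5 − 3.10 = 2.40 to 5.5 − 1.675 = 3.825 points. In the roughly 3,000 patients per database of Section 9.5, that is 72 to about 115 patients.

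**Wider range (also assumed)**

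Let p be the share of users with any of these histories and s the share of them coded within 365 days. Missed patients = 3,000 × p × (1 − s).

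- p = 2%, s = 80%: 3,000 × 0.02 × 0.20 = 12.
- p = 5%, s = 50%: 3,000 × 0.05 × 0.50 = 75 of 150.
- p = 10%, s = 20%: 3,000 × 0.10 × 0.80 = 240.

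**Effect on the AESI ratio**

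Take a true ratio R, with history patients as the whole non-compliant group. The observed ratio is R / (1 + (R − 1)f), where f = p(1 − s) / [(1 − p) + p(1 − s)] is the misplaced share of the compliant group.

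- With 2.40 points missed, f = 2.40 / (94.5 + 2.40) = 2.5%. With 3.825 points missed, f = 3.825 / (94.5 + 3.825) = 3.9%.
- R = 3 is then observed as 3 / (1 + 2 × 0.025) = 2.86 down to 3 / (1 + 2 × 0.039) = 2.78.
- Over the wider range (p from 2% to 10%, s from 20% to 80%), R = 3 is observed as 2.58 to 2.98 and R = 5 as 3.77 to 4.92.

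**The case against.** **History may itself be the exception.** Item 11 already lists bipolar disorder, anorexia nervosa, bulimia and seizure disorder as comorbidities. If item 13 used the same 365 days it would largely repeat item 11, so the authors may have meant it to reach further back. That intention is plausible, but no window is given, and the default is the only rule a programmer can follow. The sections need reconciling on either reading.

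**Figure 1 is not visible.** Section 9.3.3 refers to it, and a separate bar for history cannot be excluded. Its note b shows none. This remains an uncertainty.

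**Definitions are left to the SAP.** Section 9.3.3 leaves the final variable definitions per database to the SAP, but the 365-day default is fixed in the protocol itself.

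**A uniform window has merit.** It keeps ascertainment comparable across databases. Appendix 3 rates bipolar disorder as limited everywhere and enrolment dates as partial in the US, so a longer look-back recovers only part of the loss. This stands, and it is a reason to keep 365 days as a sensitivity analysis.

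**Feasibility.** The statement that "All citizens of these countries are represented in these national registries until death or emigration, providing virtually complete long-term follow-up" concerns follow-up. The coverage statement in Section 9.4.1 is the better support for a longer look-back.

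**Readings that go too far.** Three inferences are tempting but unsupported:

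- That 30-56% is the share of all contraindicated patients found. The denominator holds only three conditions. It omits, among others, uncontrolled hypertension, end-stage renal failure, opioid dependence and concomitant bupropion, naltrexone or MAOI.
- That the 365-day window decides which AESIs are new. Section 9.3.3 governs baseline covariates, and the protocol states no look-back for new onset.
- That the AESI comparison is badly distorted. On the assumptions above the dilution is modest, and the study has no a priori hypotheses.

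**Conclusion.** The concern holds as a badly fixed rule. Followed as written, Section 9.3.3 counts a patient as compliant when the only code for seizures, bipolar disorder, anorexia nervosa or bulimia is older than 365 days and no other criterion applies. The downward bias in the non-compliance percentage follows from the text alone.

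Its size does not. The capture figure and the 12 to 240 misplaced patients per 3,000 rest wholly on assumed prevalences and coding probabilities. The patient counts are upper figures to the extent that conditions overlap or another criterion already marks the patient as non-compliant. The AESI effect needs the further assumption that these histories raise risk, and it is secondary to the effect on primary objective 2.

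**What to change.** In Section 9.3.3 item 13, and for Section 9.7.2 criteria (b)1 (the history-of-seizures part) and (b)2, state that all data available on or before the index date are used: full registry history in the Nordic countries, and all EHR and claims history plus problem lists in the US. Keep 365 days for criteria that are not defined by history. Report the look-back length available in each database, and give the 365-day version as a sensitivity analysis. This changes only how a stated contraindication is found in the data, not any clinical rule.

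The cost is one sentence and a longer data extract. Look-back will differ between patients and databases, which the sensitivity analysis makes visible. The study is under way: Section 6 places the registry applications in September 2023 and the US final report in August 2023. Extracts already limited to 365 days before index would need extending, and the US classification might need a re-run.
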